tests will be calculated together with 95% confidence intervals. The prevalence and patterns of resistant mutations between the two treatment groups will be compared using Chi-square or Fisher's exact test. Safety analyses The number of subjects experiencing a SAE, up to 4 weeks after PZQ and AM administration will be compared between treatment groups using Fisher's exact test. Safety will be									
intervals. The prevalence and patterns of resistant mutations between the two treatment groups will be compared using Chi-square or Fisher's exact test. Safety analyses The number of subjects experiencing a SAE, up to 4 weeks after PZQ and AM administration will be compared between treatment groups using Fisher's exact test. Safety will be									
between the two treatment groups will be compared using Chi-square or Fisher's exact test. Safety analyses The number of subjects experiencing a SAE, up to 4 weeks after PZQ and AM administration will be compared between treatment groups using Fisher's exact test. Safety will be		-							
Chi-square or Fisher's exact test. Safety analyses The number of subjects experiencing a SAE, up to 4 weeks after PZQ and AM administration will be compared between treatment groups using Fisher's exact test. Safety will be									
Safety analyses The number of subjects experiencing a SAE, up to 4 weeks after PZQ and AM administration will be compared between treatment groups using Fisher's exact test. Safety will be									
The number of subjects experiencing a SAE, up to 4 weeks after PZQ and AM administration will be compared between treatment groups using Fisher's exact test. Safety will be									
The number of subjects experiencing a SAE, up to 4 weeks after PZQ and AM administration will be compared between treatment groups using Fisher's exact test. Safety will be		Safety analyses							
PZQ and AM administration will be compared between treatment groups using Fisher's exact test. Safety will be									
treatment groups using Fisher's exact test. Safety will be									
		analyzed using the all-subjects-treated approach for each time							
point separately.		point separately.							

[figure not shown]

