2. STUDY OBJECTIVES

2.1. Primary objective

The primary objective of the **SchistoSAM** (**Schisto**somiasis **S**enegal **A**rtesunate-**M**efloquine) study is to evaluate the efficacy and safety of a single course of artesunate-mefloquine (AM, intervention arm) for the treatment of schistosomiasis in Senegalese primary school-age children, compared to the standard PZQ regimen (control arm).

Endpoint measures:

- Efficacy: Parasitological cure rate (CR, as assessed by microscopy, according to WHO standard) after administration of PZQ and after one AM course (at week 4 – see study flowchart).
- Safety: Frequency and pattern of drug-related adverse events (AEs) and serious AEs (SAEs) up to 4 weeks after PZQ and AM administration.

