** Urine and stool samples will be aliquoted, preserved and shipped to ITM for further schistosomiasis diagnostic assays (eg. urine CAA lateral-flow assay – UCP-LF CAA – and a real-time stool and urine PCR) *** Throughout the trial, (S)AEs up until 4 weeks after the last administration of study medication (PZQ and AM arm) will be taken into account. In the AM arm, on the second and third administration day, this will be actively monitored. Plus, for both arms, efforts will be made to proactively monitor the adverse events within one week after PZQ and first AM administration, by an additional visit at day 7. If no contact is possible, (S)AEs will be gathered at the next scheduled study visit. More details on safety collection and reporting are described in chapter 7. A study specific SOP will be created to elaborate on the detection, the handling, and the reporting of AEs and SAEs.

Table 1: Schedule of assessments

		Screening	Recruitment	1 st admin IMP (Day 0)	1st admin IMP (Day 1 & 2³)	Follow-up AE & SAE Day 7	Parasitologic al evaluation 1	2 nd admin IMP, day 0 ³	2 nd admin IMP day 1 & 2 ³	Follow-up AE & SAE Day 7	Parasitologic al evaluation 2	3 rd admin IMP, day 0 ³	3 rd admin IMP day 1 & 2 ³	Follow-up AE & SAE Day 7	Parasitologic al evaluation 3	Intermediar efficacy evaluation	Final efficacy evaluation
Informed consent		Х															
Eligibility		Х	Х														
Demographics		Х															
Medical history			Х														
Medical evaluatio	n		Х													Х	х
Hemoglobin meas	urement		Х													Х	х
Microscopy (urine	and stool)	Х	Х				Х				х				х	Х	х
POC-CCA			Х				Х				х				х	Х	х
Urine reagent stri	o test		Х													Х	х
Fecal occult blood			х													Х	х
Ultrasound			Х													Х	х
Randomization			Х														
Concomitant med	ication check			Х	Х	Х	х	Х	х	Х	х	Х	х	Х	х	Х	х
Symptom check				Х	Х	Х	х	Х	х	Х	х	Х	х	Х	х	Х	х
Malaria diagnosis	check					Х	Х	Х		Х	х	Х		Х	Х	Х	Х
Study drug administration	AM arm			AM	AM			AM	AM			AM	AM				PZQ
	PZQ arm			PZQ													PZQ
(S)AE follo	w-up				X1	Х	Х		X1	Х	Х		X1	Х	Х		

 1 (S)AE follow-up done before second and third study drug administration.

² (S)AE follow-up done up to 4 weeks after the last study drug administration. However, efforts will be made to proactively monitor the adverse events within a week after PZQ and each AM administration, by an additional visit at day 7. If participants could not be reached, (S)AEs will be collected during the study visit. ³ Only applicable for AM arm

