8.2. Variables of interest

Primary

The primary variables to evaluate are:

- The parasitological cure rates (proportion of subjects negative for both *Schistosoma* species assessed by microscopy over total number in each arm) for AM and PZQ at week 4 after inclusion.
- The patient counts with drug-related adverse events and serious adverse events up to 4 weeks after AM and PZQ administration.

Secondary:

The secondary variables to evaluate are:

- The proportion of cured subjects (CR) of the two different arms at week 10, 16, 24 and 48 (see flowchart).
- The count of patients reporting any form of adverse event up to 4 weeks after each study drug administration.
- The egg reduction rate (ERR) at weeks 4, 10, 16, 24 and 48 (see flowchart). The ERR will be expressed as the percentage of eggs present in each subject at each time point over the number of eggs at baseline.
- The cure rate and egg reduction rate at weeks 4, 10 and 16 after first treatment administration by *Schistosoma* species and by intensity of infection.
- The result of the classic and novel diagnostic tests at baseline and at different time points, as well as a-composite reference standards.
- Clinical and laboratory characteristics related to schistosomiasis-related morbidity at baseline and at weeks 4, 10, 16, 24 and 48
- Prevalence of malaria infection at baseline and at weeks 24 and 48
- The incidence of clinical malaria during the study until week 48
- Counts of cases of anemia both pooled and by severity levels at baseline, week 24 and week
 48
- Binary variables indicating the existence of any or specific types of resistance in the sample size and among the incident malaria cases

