All non-serious and serious adverse events will be grouped according to a pre-specified side-effect coding system and tabulated. The number of subjects experiencing any adverse event, any serious adverse event, and any drug-related serious adverse event up to 4 weeks after PZQ and AM administration will be compared between treatment groups using Fisher's exact test. Safety will be analyzed using the all-subjects-treated approach for each time point separately. The safety results during the other AM administration visits will be tabulated in a similar way, but no formal statistical comparison is planned.

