Thirdly, parents of all enrolled children will be advised to bring the study ICF whenever their children need to attend the well identified study health centers at any moment during the study period, (in particular after the first and until the next AM administration) making them easily identifiable by all local health care workers. The local staff will be involved in the study, adequately informed and specifically trained to manage and report these adverse events during the preparatory period. The local investigator (medical doctor based in Richard Toll) will be immediately contacted by phone to be informed about, and provide further advice, for any problem potentially related to the study during the whole study period. Finally, medical assessment and specific queries regarding tolerance of previous administration will take place just before each subsequent AM administration. During the preparatory visits, all practicalities of the safety monitoring procedure will be established in a detailed SOP, after discussion with all local health staff.

Side effects related to PZQ are rare but may include headache, dizziness, stomach pain, nausea, tiredness, weakness, joint/muscle pain, loss of appetite, vomiting and sweating. These side effects are usually mild and temporary and may be related to some inflammatory reactions to the dying parasites. In very rare cases, more serious side effects occur such as bloody diarrhea, fever, irregular/slow heartbeat, seizures. Those side effects are short lasting and often disappear with 48h after drug administration.

Risk of favoring malaria resistance

The risk of selecting resistant parasites is extremely unlikely (or even close to non-existing) for the following reasons:

- So far, no artemisinin or partner drug resistance has been reported in large community studies conducted in high endemic areas that have evaluated ACTs for intermittent preventive treatment or seasonal malaria chemoprophylaxis ^{90–92}.
- Malaria incidence in this area is the lowest in Senegal with less than 5 cases per 1000 inhabitants, which makes it highly unlikely that the drug can be administered to a malaria patient.
- Children with clear signs of malaria or with any sign of the disease will not be eligible, making selection pressure for AM that could lead to resistance impossible, because the drug will not come into contact with plasmodium in this situation.

Loss of confidentiality

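### The primary safety variable, children with any drug-related adverse event, is missing from the listed between-arm comparisons; days 1–2 adverse-event contact in the AM arm only adds an unquantified difference in detection

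*Protocol*

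**What the plan says.** Protocol section 2.1 puts safety beside efficacy in the primary objective: "Safety: Frequency and pattern of drug-related adverse events (AEs) and serious AEs (SAEs) up to 4 weeks after PZQ and AM administration". Section 8.2 turns this into a primary variable: "The patient counts with drug-related adverse events and serious adverse events up to 4 weeks after AM and PZQ administration". The count of patients with any form of AE is listed separately there, as a secondary variable.

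Section 8.3.4, under safety analyses, begins with description: "All non-serious and serious adverse events will be grouped according to a pre-specified side-effect coding system and tabulated". It then names three counts, "any adverse event, any serious adverse event, and any drug-related serious adverse event up to 4 weeks after PZQ and AM administration", which "will be compared between treatment groups using Fisher's exact test". The synopsis is narrower: "The number of subjects experiencing a SAE, up to 4 weeks after PZQ and AM administration will be compared between treatment groups".

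On how AEs are found, section 7.1 applies a set questionnaire at the supervised dosing visits, on day 7 and at week 4. Section 5.1 and Table 1 (footnote 3) give the day 1 and day 2 visits to the AM arm only. The note to section 5.1 adds: "In the AM arm, on the second and third administration day, this will be actively monitored". The day 7 contact is for both arms but is described as an effort; if it fails, events are gathered at the next scheduled visit.

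**The concern.** The variable defined as primary for safety and the variables listed for comparison do not match. The third item in section 8.3.4 covers only the serious subset of drug-related events. A statistician who follows the list would deliver comparisons of any AE, any serious AE and drug-related serious AE, but none for the count of children with a drug-related AE. Safety is half of the primary objective, and most drug reactions that bear on tolerability are likely to be non-serious.

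The second issue concerns how any comparison of AEs is read. During the first course, AM children are asked about AEs on two days when PZQ children are not seen. Mild, passing events are more likely to be recorded when asked about the next day than when recalled a week later. The expected direction is relatively more recorded AEs under AM. Serious AEs should be little affected.

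**Working it through.** **Variable against comparison.**

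| Place | Drug-related AE, any seriousness | Any AE | Any serious AE | Drug-related serious AE |
|---|---|---|---|---|
| 2.1, primary endpoint | yes | – | yes | – |
| 8.2, primary variable | yes | – | yes | – |
| 8.3.4, Fisher comparisons | **no** | yes | yes | yes |
| Synopsis, Fisher comparison | **no** | no | yes | no |

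The first column is filled where the variable is defined and empty where it is compared. Section 8.3.4 also has a general sentence on comparing proportions, but it stands among the secondary analyses, and the safety paragraph has its own explicit list. The gap is therefore in the text as written.

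**AE contacts in the first course** (sections 5.1 and 7.1).
- AM: day 0, day 1, day 2, day 7, week 4 = 5.
- PZQ: day 0, day 7, week 4 = 3.

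**What the unequal contact could do.** The protocol states no AE risk for the trial, no recall rate, and no power or alpha for safety. There is no plan figure to reproduce, and the following is illustration only. Inputs:
- n = 363 treated per arm (section 4.3).
- The same true AE risk r in both arms (assumed).
- Full detection under AM and a fraction d detected under PZQ (assumed, d = 70%, range 50–90%).
- Two-sided Fisher test at 5% (alpha assumed).

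Apparent excess under AM = r − r·d = r(1 − d). For r = 20% and d = 70%: 0.20 × 0.30 = 6 points. The probability that Fisher's test rejects is summed exactly over the two binomial distributions.

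| True risk r | Excess at d = 70% (90% to 50%) | Fisher rejects at d = 70% (90% to 50%) |
|---|---|---|
| 1% | 0.3 points (0.1 to 0.5) | 2% (2% to 4%) |
| 2% | 0.6 points (0.2 to 1.0) | 5% (3% to 12%) |
| 5% | 1.5 points (0.5 to 2.5) | 13% (4% to 36%) |
| 20% | 6 points (2 to 10) | 54% (9% to 96%) |

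Detection in the AM arm need not be complete. At r = 20% with 95% detection under AM, PZQ detection of 85%, 75% and 65% gives an excess of 2, 4 and 6 points and rejection in 9%, 26% and 56% of simulated trials. With equal detection of 95% in both arms, rejection is about 4%.

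**Why an interval beside the p-value.** With no serious AE among 363 PZQ children, 5 of 363 under AM gives Fisher p = 0.062 and 6 of 363 gives p = 0.031. For rare events the p-value alone shows little about what difference the data exclude.

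**The case against.** **The mismatch may be a one-word slip.** Drug-related serious AE may have been meant as drug-related AE. The primary endpoint is phrased as frequency and pattern, section 8.1 states no safety hypothesis, all AEs are tabulated, and every drug-related AE is contained in the any-AE comparison. In an open-label trial with causality judged by the study physician, any AE is arguably the sturdier measure. This stands in part. A reader might infer that non-serious drug-related AEs enter no comparison at all, or that the safety objective goes untested. The documents do not support that: these events count within any AE, and serious AEs are tested. What remains is that the variable named as primary has no comparison of its own and that three places in the protocol disagree.

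**The bias is not established in size.** A reader might infer a large, known bias. The protocol does not support this. Section 11.6.1 calls PZQ side effects rare, and section 1.1.1 puts mefloquine-related AEs at 1–2%; at such risks the distortion is small. All-cause AE risk over four weeks may be higher, but no figure is given. Both arms also have observed dosing with at least 30 minutes' follow-up, the emergency number, trained local nurses, and the day 7 and week 4 questions. AM events after the third dose rely on day 7 recall too.

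**PZQ effects said to vanish within 48 hours.** The sentence "Those side effects are short lasting and often disappear with 48h after drug administration" directly follows the very rare, more serious effects. The common ones are described only as usually mild and temporary. It does not show that ordinary PZQ reactions are gone within two days.

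**Restricting the formal test to day 7 and week 4.** This looks like a clean remedy but is not. Section 11.6.1 says mefloquine toxicity usually appears early and is acute. Dropping events reported on days 1–2 could remove real AM events and favour AM. The restriction belongs in a sensitivity analysis only.

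**Misreading a large p-value.** Nothing in the protocol plans to read a non-significant Fisher test as equal safety. The interval is recommended for its information, not to correct a stated error.

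**Conclusion.** The omission holds as the protocol is written: any drug-related AE is a primary safety variable in sections 2.1 and 8.2 and is absent from the comparisons in section 8.3.4 and the synopsis. This conclusion rests on the text alone and needs no assumption.

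The unequal AE contact on days 1–2 is also a fact of the schedule. It makes an upward shift in recorded AM events plausible, mainly for mild and transient ones. Its size cannot be derived from the protocol. Under the assumptions above, the excess is at most 1 point at true risks of 1–2% and could be material at about 20%, depending on recall. The extra AM visits follow from three-day dosing and are not themselves a fault. The efficacy analysis is untouched.

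**What to change.** 1. In section 8.3.4, add any drug-related adverse event (serious or not), up to 4 weeks after PZQ and first AM administration, to the between-arm comparisons. Keep the three already listed.
2. For each, give the risk difference with a 95% confidence interval beside Fisher's p-value.
3. Bring the synopsis into line with section 8.3.4, and carry the same list into the SAP before it is final.
4. Keep AEs from all contacts in the main comparison. Add a sensitivity analysis limited to AEs elicited at contacts common to both arms (day 0, day 7, week 4).
5. State the unequal contact on days 1–2 when interpreting the AE results, including that the restricted analysis can miss early AM events.

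The cost is a few lines of wording, one extra analysis, and a database flag for the contact at which each AE was elicited. No visit, dose or clinical rule changes.

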12. DISSEMINATION OF RESULTS, INTELLECTUAL PROPERTY

All study documents are provided by the Sponsor to the Investigators and his/her appointed staff in confidence. None of this material may be disclosed to any party not directly involved with the study, without written permission from the Sponsor.

Data sharing has become increasingly important to enable further analyses and broaden scientific collaborations beyond the initial collaborators. This is especially true for neglected tropical diseases, such as schistosomiasis, where robust data from well-structured clinical trials are limited. This process of data sharing involves ensuring the harmonization of data quality, the protection of the confidentiality of participants and communities, and fair scientific credit to the country where the data originated. The project will evaluate the possible repositories or collaborative platforms where anonymized final data can be shared, according to the general policies of the parties involved in this study.

The dissemination and exploitation activities in SchistoSAM will be coordinated by the project management team (composed of CTU experts, ITM supervisors and IRESSEF investigators), based on a central Dissemination and Communication plan, and guided by the results of the trial, and the additional laboratory workup.

The main scientific output will be an **independent evaluation of AM's safety and efficacy** (both of single and repeated courses) against schistosomiasis compared to that of PZQ. As already underlined, if the efficacy is found equal (at least non-inferior) to that of PZQ, it could be considered a valuable second-line treatment for schistosomiasis (considering its 3-day duration), taking into account the specificity of each region. This should lead to a high impact publication in a major Infectious Diseases Journal and open the way to additional confirmative/complementary clinical studies in other settings. In case the trial results are negative, it will also be important to publish the data, which would then probably discard AM as an alternative therapeutic option and allow researchers to fully focus on other novel treatments.

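### Safety is part of the primary objective, but the only between-arm method named for it is Fisher's exact test, with no risk difference or confidence interval to show what excess harm is excluded

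*Protocol*

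**What the plan says.** Section 2.1 of the protocol makes safety part of the primary objective, with the endpoint "Frequency and pattern of drug-related adverse events (AEs) and serious AEs (SAEs) up to 4 weeks after PZQ and AM administration". Section 8.2 repeats it as a primary variable in count form: "The patient counts with drug-related adverse events and serious adverse events up to 4 weeks after AM and PZQ administration".

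The safety paragraphs of section 8.3.4 fix the analysis. "All non-serious and serious adverse events will be grouped according to a pre-specified side-effect coding system and tabulated". Three counts of children (any AE, any SAE, and "any drug-related serious adverse event up to 4 weeks after PZQ and AM administration will be compared between treatment groups using Fisher's exact test") are then tested. On the population, "Safety will be analyzed using the all-subjects-treated approach for each time point separately". For the later AM courses the events are tabulated and "no formal statistical comparison is planned", so the comparison after PZQ and the first AM course is the only formal one. The synopsis also names only Fisher's exact test, and there only for SAEs.

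The other primary endpoint is handled differently. Section 8.3.3 gives cure a two-sided 95% interval for the difference in proportions by Wilson's score method, a margin of -10 points and a rule for reading the interval. Section 4.3 bases the sample size on the cure rate only: 300 per arm, raised to 363 per arm (726 in total) for loss to follow-up.

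**The concern.** For a safety question the useful result is how large an excess of harm the data still allow. A test of equality does not answer that. When events are few, a large p-value is compatible both with no excess and with an excess that would matter.

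This matters here because the background (section 1.1.1) names serious neuropsychiatric effects of mefloquine as the concern, and section 12 presents AM's safety, together with its efficacy, as the trial's main output. With the method as named, 4 SAEs on AM against 1 on PZQ would yield p = 0.37 and no statement about size. The protocol already computes an interval for cure, so the tool is at hand but is not applied to safety.

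**Working it through.** **Inputs from the protocol.** 300 evaluable and 363 recruited per arm, 80% power, and cure rates of 75% and 65%, that is, a 10-point margin (section 4.3). Two-sided 95% interval by Wilson's score method (section 8.3.3). Safety in all treated children (section 8.3.4). I take n = 363 per arm, the best case in which every recruited child is treated.

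**Inputs that are assumptions.** The protocol gives no SAE rate, so a range is shown. Its background figure of 1-2% concerns adverse events generally. The Fisher test is taken as two-sided at 0.05. The score interval for a difference is taken as the Newcombe form, which combines the two Wilson limits.

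**1. The plan's own figure.** With a true cure rate of 75% in both arms, n = 2 × 0.75 × 0.25 × (1.960 + 0.842)² / 0.10² = 0.375 × 7.849 / 0.01 = 294.3, so 295 per arm. The stated 300 is reproduced, and it is a cure-rate figure only. No safety figure is stated to reproduce.

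**2. Smallest significant result against zero.** At 363 per arm, 5 v 0 gives p = 0.062 and 6 v 0 gives p = 0.031. At least 6 events are therefore needed.

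**3. Power.** Against a PZQ rate of 0%, power is P(X ≥ 6) with X binomial(363, AM rate). Otherwise it is the sum of the two binomial probabilities over all outcomes with p < 0.05.

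| Assumed rate, AM v PZQ | Power at 363 per arm |
|---|---|
| 0.5% v 0% | 1% |
| 1% v 0% | 16% |
| 1.5% v 0% | 46% |
| 2% v 0% | 73% |
| 2.2% v 0% | about 80% |
| 2.5% v 0% | 89% |
| 2% v 1% | 12% |
| 3% v 1% | 39% |
| 4% v 1% | 69% |
| 15% v 10% | 49% |
| 20% v 10% | 96% |
| 30% v 20% | 86% |

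**4. What an interval would add.** With p1, p2 the observed proportions on AM and PZQ, d = p1 − p2 and Wilson limits (l1, u1) and (l2, u2):

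lower = d − √[(p1 − l1)² + (u2 − p2)²]; upper = d + √[(u1 − p1)² + (p2 − l2)²].

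For 4 v 1: p1 = 1.102%, u1 = 2.799%, p2 = 0.275%, l2 = 0.049%, d = 0.826. Upper = 0.826 + √(1.697² + 0.226²) = 0.826 + 1.712 = 2.54 points.

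| SAEs, AM v PZQ | Difference, points | 95% interval, points | Fisher p |
|---|---|---|---|
| 0 v 0 | 0.0 | −1.05 to +1.05 | 1.00 |
| 3 v 0 | +0.8 | −0.4 to +2.4 | 0.25 |
| 4 v 1 | +0.8 | −0.6 to +2.5 | 0.37 |
| 5 v 0 | +1.4 | +0.07 to +3.2 | 0.062 |
| 6 v 0 | +1.7 | +0.3 to +3.6 | 0.031 |

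The 5 v 0 row shows that the two methods can disagree: the interval excludes zero while Fisher's test is not significant.

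**The case against.** The strongest reply has four parts.

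- **No decision rule is affected.** The protocol states non-inferiority for efficacy only, and the safety endpoint is worded as frequency and pattern. A reader might infer that a non-significant Fisher test will be taken as proof that AM is as safe as PZQ. The documents do not support that: no section says so, and no safety hypothesis or margin exists. This stands, and the point is limited to what the named output can and cannot show.

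- **The test is not blind to all serious harm.** A reader might also infer that it would miss most of it. That depends on the rate assumed: power is 73% for 2% v 0%, 89% for 2.5% v 0%, and high for large differences in common events (96% for 20% v 10%). This stands too. The weakness lies at SAE rates up to about 1% and at a doubling from 1% to 2%.

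- **Other safety information exists.** Events are tabulated, severity and causality are graded, and the Data and Safety Monitoring Board sees every SAE report (section 7.2). A reader could derive an interval from the counts. This is true, but it does not make the interval the pre-specified primary safety result.

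- **It could be left to the SAP, which is not at hand.** The SAP may well add an interval. Yet the protocol is not silent: it selects the method for a primary endpoint, and section 8.3.4 and the synopsis both name the test without an estimate.

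It is also fair to say that an interval creates no extra information about rare events, and that it can conflict with Fisher's test. The first is a limit of the sample size. The second means that the fix must say which result governs.

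**Conclusion.** The point holds in a limited form. For a primary safety comparison the protocol names a p-value and a tabulation, with no effect estimate or interval. At 363 per arm the test has 1% to 16% power for an AM SAE rate of 0.5% to 1% against zero and 12% for 2% against 1%, with 80% reached only near 2.2% against zero. An interval would show that even 0 v 0 leaves room for an excess of about 1.0 point, and 4 v 1 for 2.5 points.

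The power figures rest on assumed SAE rates, on all 363 children per arm being treated, and on a two-sided 0.05 level. The lack of an estimate or interval in the protocol's safety methods does not depend on those assumptions. This is a change that should be made. It does not undermine the trial.

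**What to change.** In section 8.3.4 and the matching synopsis text:

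- Make the reported safety comparison, for each listed AE and SAE category, the difference in proportions (AM minus PZQ) with a two-sided 95% confidence interval by the score method already used for cure.
- Base the safety wording on that interval, in particular on the upper limit, that is, the excess which the data exclude.
- State that a non-significant Fisher test is not read as equal safety.
- Keep Fisher's p-value as a labelled supplement, and state that the interval governs where the two disagree.

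The cost is a few sentences and slightly more reporting. No children, visits or data are added. The safety statement will be less favourable when events are few, because the upper limit will be in plain view.
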